6.4.3 Prohibited concomitant therapy

Anti-neoplastic therapies

Treatment with systemic anticancer agents (chemotherapy, hormone therapy, targeted or biologic agents) other than the protocol treatment is not permitted until disease progression is documented per RECIST. Palliative radiotherapy or surgery may be allowed and should be discussed with Novartis prior to administration.

6.4.4 Use of Bisphosphonates (or other concomitant agents)

Not applicable.

6.5 Patient numbering, treatment assignment or randomization

6.5.1 Patient numbering

Each patient is identified in the study by a Subject Number (Subject No.), that is assigned when the patient is first enrolled for screening and is retained as the primary identifier for the patient throughout his/her entire participation in the trial. The Subject No. consists of the Center Number (Center No.) (as assigned by Novartis to the investigative site) with a sequential patient number suffixed to it, so that each subject is numbered uniquely across the entire database. Upon signing the informed consent form, the patient is assigned to the next sequential Subject No. available to the investigator.

Once assigned to a patient, the Subject No. will not be reused.

6.5.2 Treatment assignment or randomization

6.5.3 Not applicable. Treatment blinding

This study is an open-label study, thus it is not applicable.

6.6 Study drug preparation and dispensation

The investigator or responsible site personnel must instruct the patient or caregiver to take the study drugs as per protocol. Study drug(s) will be dispensed to the patient by authorized site personnel only. All dosages prescribed to the patient and all dose changes during the study must be recorded on the Dosage Administration Record CRF.

Table 6-4 Preparation and dispensing

Study treatments	Dispensing	Preparation
Afinitor	Tablets including instructions for administration are dispensed by study personnel on an outpatient basis. Patients will be provided with adequate supply of study treatment for self-administration at home until at least their next scheduled study visit.	Not applicable

6.6.1 Study drug packaging and labeling

Study treatment, [everolimus], will be sourced as local commercial supply (in the locally approved formulation and packaging configuration) and labeled in the country when possible.

The study medication packaging has a 2-part label. A unique medication number is printed on each part of this label which corresponds to the treatment arm and a specific visit. Responsible site personnel will identify the study treatment package(s) to dispense to the patient and obtaining the medication number(s). Site personnel will add the patient number on the label. Immediately before dispensing the package to the patient, site personnel will detach the outer

part of the label from the packaging and affix it to the source document (Drug Label Form) for that patient's unique patient number.

Medication labels will be in the local language and comply with the legal requirements of each country. They will include storage conditions for the drug and the medication number but no information about the patient.

Everolimus tablet, 2.5mg/tablet, 5 mg/ tablet, 1 tablet per blister

6.6.2 Drug supply and storage

Everolimus tablet will be supplied by Novartis, and it must be received by designated personnel at the study site, handled and stored safely and properly, and kept in a secured location to which only the investigator and designated site personnel have access. Upon receipt, the **study treatment** should be stored according to the instructions specified on the drug labels and in the Chinese PI.

6.6.3 Study drug compliance and accountability

6.6.3.1 Study drug compliance

Compliance will be assessed by the investigator and/or study personnel at each patient visit and information provided by the patient and/or caregiver will be captured in the Drug Accountability Form. This information must be captured in the source document at each patient visit.

- All doses taken by the patient and all dose changes during the study must be recorded on the Dosage Administration Record CRF.
- The investigator or his/her designee must keep documentation (overall drug accountability log for the study as well as individual study drug accountability records for each patient) of tablets administered, tablets used, dose changes, dates dispensed and intervals between visits.
- Drug accountability will be monitored by the field monitor during site visits and at the completion of the study.

6.6.3.2 Study drug accountability

The investigator or designee must maintain an accurate record of the shipment and dispensing of study treatment in a drug accountability log. Drug accountability will be noted by the field monitor during site visits and at the completion of the study. Patients will be asked to return all unused study treatment and packaging on a regular basis, at the end of the study or at the time of study treatment discontinuation.

At study close-out, and, as appropriate during the course of the study, the investigator will return all used and unused study treatment, packaging, drug labels, and a copy of the completed drug accountability log to the Novartis monitor or to the Novartis address provided in the investigator folder at each site.

6.6.3.3 Handling of other study treatment

Not applicable.

6.6.4 Disposal and destruction

The study drug supply can be destroyed at the local Novartis facility, Drug Supply group or third party, as appropriate.

7 Visit schedule and assessments

7.1 Study flow and visit schedule

[Table 7-1](#) lists all of the assessments and indicates with an “X”, the visits when they are performed. All data obtained from these assessments must be supported in the patient’s source documentation.

No CRF will be used as a source document.

The table indicates which assessments produce data to be entered into the clinical database (D) or remain in source documents only (S) (“Category” column). Tests, procedures and visits should occur on schedule whenever possible. However, tests, procedures, and visits that occur outside the prescribed allowable windows indicated in [Table 7-1](#) will not constitute protocol deviations.

Table 7-1 Visit evaluation schedule

	Category	Protocol Section 7.2	Screening/ Baseline (-28~0day)	Visit 1 (day1)	Visit 2 (day28±2d)	Visit 3 (week 12±1wk)	Subsequent visits (every 12wk±1wk)	End of study treatment (EOT)	30-day Safety Follow-up	Survival follow up (every 6 months)
Obtain Informed Consent	D		X							
Patient history	D		X							
Demography	D		X							
Inclusion/exclusion criteria	D		X							
Relevant medical history/current medical conditions	D		X							
Diagnosis of cancer	D		X							
Prior/concomitant medications	D		X	X	X	X	X	X		
Physical examination	S	7.2.2.1	X	X	X	X	X	X		
Vital signs	D	7.2.2.2	X	X	X	X	X	X		
Height/Weight	D	7.2.2.3	X							
Laboratory assessments		7.2.2.4								
Hematology ^a	D	7.2.2.4.1	X	X	X	X	X	X		
Liver function tests ^b	D	7.2.2.4.2	X		X	X	X	X		
Coagulation	S	7.2.2.4.3	X		X	X	X	X		
Other laboratory test ^c	S	7.2.2.4.6		Only to be done if clinically indicated						
Urinalysis ^c	S	7.2.2.4.4	X	Only to be done if clinically indicated						
Pregnancy test ^d	D	7.2.2.4.5	X					X		
Tumor evaluation(MRI or CT) ^e	D	7.2.1	X			X	X			X ^f
Pulmonary function tests, Chest CT ^g	D	7.2.2.5		Only to be done if clinically indicated						
Adverse events	D		X	Continuously					X	
Study Drug administration	D			X	X	X	X	X		

7.1.1 Molecular pre-screening

Not applicable.

7.1.2 Screening

Screening examination must include serum hCG laboratory test ([Section 5.3](#) exclusion criteria-4), and confirmation of diagnosis according to inclusion criteria.

Informed consent must be signed prior to any screening procedure.

Re-screening is allowed for no more than 3 times within 6 months only when the previous severe and/or uncontrolled medical conditions mentioned in [Section 5.3](#) Exclusion Criteria (except for bullet point 1, 5 and 8) has been resolved.

7.1.2.1 Eligibility screening

Not applicable.

7.1.2.2 Information to be collected on screening failures

Patients who sign an informed consent but fail to be started on treatment for any reason will be considered as screen failure. The reason for not being started on treatment will be entered on the Screening Phase Disposition Page. The demographic information, informed consent, and Inclusion/Exclusion pages must also be completed for Screen Failure patients. No other data will be entered into the clinical database for patients who are screen failures, unless the patient experienced a Serious Adverse Event during the Screening Phase (see [Section 8](#) for SAE reporting details).

7.1.2.3 Patient demographics and other baseline characteristics

Data will be collected on patient characteristics including demographic information (age, sex, race, weight, height) and other background or relevant medical history (disease history, family history of disease, prior anti-neoplastic therapies, and any other assessments that are done for the purpose of determining eligibility for inclusion in the study [i.e., complete physical examination, pregnancy test for women of child-bearing potential, CT/MRI]).

Medical history will include family history of disease.

7.1.3 Run-in period

Not applicable.

7.1.4 Treatment period

Patients will start study treatment at Visit 1 (Treatment Day 1) and continue to be treated per protocol until documentation of disease progression, unacceptable toxicity, death, withdrawal of consent or sponsor decision to stop the study. However, study treatment may prematurely be discontinued for other reasons as well. Please refer to [Section 7.1.5](#). And patients should follow the visit schedule in [Table 7-1](#). If the patient is still on treatment after 2 years, he/she will be shifted to commercial drug.

7.1.5 Discontinuation of study treatment

Patients may voluntarily discontinue from the study treatment (everolimus) for any reason at any time. If a patient decides to discontinue from the study treatment (everolimus) the investigator should make a reasonable effort (e.g. telephone, e-mail, letter) to understand the primary reason for this decision and record this information in the patient's chart and on the appropriate CRF pages. They may be considered withdrawn if they state an intention to withdraw, fail to return for visits, or become lost to follow-up for any other reason.

The investigator may discontinue study treatment (everolimus) for a given patient if, he/she believes that continuation would be detrimental to the patient's well-being.

The term "interruption" refers to a patient stopping the study medication during the course of the study, but then re-starting it at a later time in the study.

The term "discontinuation" refers to a patient's premature and permanent withdrawal from the study treatment. The reason for discontinuation from treatment will be recorded.

At the time patients discontinue study treatment, a visit should be scheduled as soon as possible, at which time all of the assessments listed for the End of Treatment (EOT) visit will be performed. An End of Treatment Phase Disposition CRF page should be completed, giving the date and reason for stopping the study treatment.

At a minimum, all patients who discontinue study treatment, including those who refuse to return for a final visit, will be contacted for safety evaluations during the 30 days following the last dose of study treatment.

For criteria for premature withdrawal refer to [Section 7.1.6](#).

End of treatment/Premature withdrawal visit is not considered as the end of the study.

7.1.5.1 Replacement policy

Not applicable.

7.1.6 Withdrawal of consent

Patients may voluntarily withdraw from the study or be dropped from it at the discretion of the investigator at any time. Patients may be withdrawn from the study if any of the following occur:

- pregnancy;
- discovery of patient ineligibility;

In addition to the general withdrawal criteria, the following study specific criteria will also require study treatment discontinuation:

- Any other protocol deviation that results in a significant risk for the patient's safety
- Subject withdrew consent
- Lost to follow-up
- Administrative problems
- Adverse events including laboratory abnormalities which required discontinuation of study treatment listed in [Table 6-1](#);

- Compliance problems other than dose interruption as described above;
- Unsatisfactory therapeutic effect as the investigator consider the subject's condition no longer benefit from study treatment (be specified in the CRF)
- Use of prohibited treatment

If a patient has discontinued the study drug due to an unacceptable adverse event (AE) or an abnormal laboratory value, he/she should not have withdrawal of consent recorded as the reason for discontinuation. Instead, the reason for discontinuation must be recorded as due to an AE or abnormal laboratory value.

7.1.7 Follow up for safety evaluations

All patients must have safety evaluations for 30 days after the last dose of study treatment.

Data collected should be added to the Adverse Events CRF and the Concomitant Medications CRF.

7.1.8 Lost to follow-up

For patients whose status is unclear because they fail to appear for study visits without stating an intention to withdraw consent, the investigator should show "due diligence" by contacting the patient, family or family physician as agreed in the informed consent and by documenting in the source documents steps taken to contact the patient, e.g. dates of telephone calls, registered letters, etc. A patient should not be considered lost to follow-up until due diligence has been completed. Patients lost to follow up should be recorded as such on the appropriate Disposition CRF.

7.2 Assessment types

7.2.1 Efficacy assessments

Tumor assessments are to be performed for screening purposes and are needed to determine the eligibility of the patient. Last available results of scans performed within 28 days prior to first dose of study drug will be used as baseline values. Negative scans at screening need not be repeated unless warranted by signs and symptoms suggesting disease progression. The assessment data will be collected until disease progression, unacceptable toxicity, death, protocol deviation or other reason that may leads to discontinuation or the end of study.

The following tumor assessments are to be performed and assessed prior to enrollment:

- Abdominal and pelvic triphasic CT or multiphase MRI;
- Chest X-ray (and/or chest CT if disease is present in chest).

To determine eligibility, measurable and non-measurable lesions must be assessed and target lesions identified prior to enrollment. For definition of measurable and target lesions please refer to RECIST 1.1 ([Appendix 1](#))

The same method of assessment and the same technique should be used to characterize each identified and reported lesion at baseline and after every 12 weeks while on-study. All radiology evaluations will be performed initially by the local radiologist.

Details of response assessment are provided in full protocol based on RECIST1.1, and are based exclusively on radiological findings obtained at tumor assessments.

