4.1 Description of study design

Patient who are eligible will be provided with everolimus by sponsor to treat pNET and will follow the visit schedule in [Table 7-1](#) to collect safety and efficacy data until disease progression, unacceptable toxicity, death, protocol deviation or other reason that may lead to discontinuation before the end of study. All patients will be followed-up for survival status every 6 months by the investigator until death, lost to follow-up, withdrawal of consent for survival or end of study. If the patient is still on treatment after 2 years, he/she will be shifted to commercial drug. However, this shift has no impact on participation in the study, all assessments will continue as before.

Figure 4-1 Study design

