14.1.19 Progression-free survival

Usually in all Oncology studies, patients are followed for tumor progression after discontinuation of study medication for reasons other than progression or death. If this is not used, e.g. in Phase I or II studies, this should be clearly stated in the protocol. Note that randomized trials (preferably blinded) are recommended where PFS is to be the primary endpoint.

Progression-free survival (PFS) is the time from date of randomization/start of treatment to the date of event defined as the first documented progression or death due to any cause. If a patient has not had an event, progression-free survival is censored at the date of last adequate tumor assessment.

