².=After the last adequate tumor assessment. "Date of next scheduled assessment" is defined in Section 14.1.25.

³.=The rare exception to this is if the patient dies no later than the time of the second scheduled assessment as defined in the protocol in which case this is a PFS event at the date of death.

The primary analysis and the sensitivity analyses must be specified in the protocol. Clearly define if and why options (1) are not used for situations C, E and (if applicable) F.

Situations C (C1 and C2): Progression or death after one or more missing assessments: The primary analysis is usually using options (1) for situations C1 and C2, i.e.

- (C1) taking the actual progression or death date, in the case of only one missing assessment.
- (C2) censoring at the date of the last adequate assessment, in the case of two or more consecutive missing assessments.

In the case of two or missing assessments (situation C2), option (3) may be considered jointly with option (1) in situation C1 as sensitivity analysis. A variant of this sensitivity analysis consists of backdating the date of event to the next scheduled assessment as proposed with option (2) in situations C1 and C2.

Situation E: Treatment discontinuation due to ‘Disease progression’ without documented progression: By default, option (1) is used for situation E as patients without documented PD should be followed for progression after discontinuation of treatment. However, option (2) may be used as sensitivity analysis. If progression is claimed based on clinical deterioration instead of tumor assessment by e.g. CT-scan, option (2) may be used for indications with high early progression rate or difficulties to assess the tumor due to clinical deterioration.

Situation F: New cancer therapy given: the handling of this situation must be specified in detail in the protocol. However, option (1), i.e. censoring at last adequate assessment may be used as a default in this case.

Additional suggestions for sensitivity analyses

Other suggestions for additional sensitivity analyses may include analyses to check for potential bias in follow-up schedules for tumor assessments, e.g. by assigning the dates for censoring and events only at scheduled visit dates. The latter could be handled by replacing in [Table 14-5](#) the “Date of last adequate assessment” by the “Date of previous scheduled assessment (from baseline)”, with the following definition:

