- d. A serum pregnancy test will be conducted locally at screening/baseline in all females of child-bearing potential, urine pregnancy test will be conducted at the end of treatment visit.
- e. Repeat scans (multiphase MRI or triphasic CT) at baseline and every 12 weeks thereafter. The same type of scan should be used at baseline and follow-up.
- f. Efficacy assessment will be collected until progression of disease (PD).
- g. If an investigator suspects a patient may be developing non-infectious pneumonitis, investigations such as pulmonary function tests, CT chest and referral to a pulmonologist should be considered.

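### The plan gives two rules for whether tumour scans continue after everolimus is stopped without progression; following the one that ends them adds PFS censoring that is informative if risk changes after stopping.

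*Protocol*

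**What the plan says.** **Text that ends collection when treatment stops**

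- Protocol 7.2.1: "The assessment data will be collected until disease progression, unacceptable toxicity, death, protocol deviation or other reason that may leads to discontinuation". The sentence goes on to add the end of study as a further end point.
- Protocol 4.1: patients follow the visit schedule "to collect safety and efficacy data until disease progression, unacceptable toxicity, death, protocol deviation or other reason that may lead to discontinuation". The next sentence provides for six-monthly follow-up of survival status only.
- SAP section 3 repeats 4.1, with visit deviation in place of protocol deviation.

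**Text that continues it to progression**

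- Protocol Table 7-1: the row "Tumor evaluation(MRI or CT) ^e" has no mark at end of treatment, but has a mark with footnote f under survival follow-up. The wording of footnote f can be read only in the SAP's copy of the schedule (SAP Appendix 1): "Efficacy assessment will be collected until progression of disease (PD").
- Protocol 7.2.1 also asks for the same imaging "at baseline and after every 12 weeks while on-study", and 7.1.5 adds: "End of treatment/Premature withdrawal visit is not considered as the end of the study".
- Protocol Appendix 1, section 14.1.19, describes as usual that "patients are followed for tumor progression after discontinuation of study medication for reasons other than progression or death", and asks for a clear protocol statement where this is not done. Section 14.1.27, situation E, adds that "patients without documented PD should be followed for progression after discontinuation of treatment".

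**What the SAP does with the data (Table 2)**

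- Row 4: no event, censored at the last adequate assessment.
- Row 3: clinical progression leading to end of treatment is an event.
- Row 5: new anticancer therapy is censored at the last adequate assessment before it.
- Rows 6 and 7 with note b: death is an event, but progression or death more than 26 weeks (24 + 2) after the last assessment is censored.

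**The concern.** A site that relies on 4.1 and 7.2.1 would stop imaging a patient who comes off everolimus for toxicity and collect survival only. A site that relies on the schedule would keep imaging. Nothing in either document says which text prevails.

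Under the first reading, the reason for stopping treatment also decides whether a later progression can be seen. If the risk of progression differs after stopping, censoring at the stop is informative and the Kaplan-Meier curve no longer estimates time from first dose to progression or death. Protocol 2.2 chose PFS to match the primary endpoint of study C2324, so a PFS that depends on which paragraph a site followed weakens that comparison. The SAP has no sensitivity analysis for this; its only efficacy sensitivity analysis concerns COVID-19 (SAP 5.5.5).

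**Working it through.** The plan gives no figure to reproduce. The sample size rests on feasibility and PFS is described, not tested. The check has three parts.

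**1. Who is affected if scans end when treatment stops (SAP Table 2)**

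- Stops without RECIST or clinical progression, no later event recorded: censored at the last adequate scan (row 4). These events are lost.
- Same patient, death more than 26 weeks after the last scan: also censored (row 7). Note b sets the limit by elapsed time, so it applies whether or not scans were still required.
- Same patient, death within 26 weeks of the last scan: still an event (rows 6 and 7).
- Stops for clinical progression: still an event (row 3).
- Starts new anticancer therapy: censored under either rule (row 5).

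**2. Size of the effect on the median**

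Inputs from the documents: the C2324 medians of 11.04 months (everolimus) and 4.60 months (placebo) in Protocol 1.2.1.2, and about 60 patients (10.8). Assumed: exponential times; a share p of 10%, 20% or 30% stopping for non-progression reasons before a PFS event; and the hazard after stopping.

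Let λ1 = ln 2 / 11.04 = 0.0628 per month (on drug), λ2 the hazard after stopping, and τ = λ1·p/(1−p) the stopping rate, which makes p the share who stop first. Time from first dose to progression or death then has

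S(x) = exp(−(λ1+τ)x) + [τ/(λ1+τ−λ2)]·[exp(−λ2x) − exp(−(λ1+τ)x)].

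For p = 0.2 and λ2 = ln 2 / 4.60 = 0.1507: τ = 0.0157, λ1+τ = 0.0785, and S(x) = 0.5 at x = 10.20 months. Censoring at the stop makes Kaplan-Meier estimate 11.04, so the overstatement is 11.04 − 10.20 = 0.84 months.

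| Post-stop assumption | True median, p = 10 / 20 / 30% | 11.04 minus true median |
|---|---|---|
| median 4.60 months (ratio 2.4) | 10.63 / 10.20 / 9.74 | +0.4 / +0.8 / +1.3 |
| hazard ratio 1.5 | 10.86 / 10.66 / 10.43 | +0.2 / +0.4 / +0.6 |
| median 8 months (ratio 1.38) | 10.90 / 10.74 / 10.56 | +0.1 / +0.3 / +0.5 |
| hazard unchanged | 11.04 / 11.04 / 11.04 | 0 / 0 / 0 |
| hazard ratio 0.75 | 11.15 / 11.29 / 11.46 | −0.1 / −0.3 / −0.4 |

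Upper bound on lost events: 60 × 0.1, 0.2, 0.3 = 6, 12, 18.

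The formula censors at the stop, whereas row 4 back-dates to the last scan. A simulation with 12-weekly scans, a 60-month cutoff, no deaths before progression and post-stop hazard ratios from 0.75 to 3 includes that. Per 60 patients, observed events fall from about 57 to 60 with follow-up to progression to about 53, 47 or 42 when scans end at the stop. At 30% stopping, 12-month PFS moves by −2.5 points (0.513 to 0.488, ratio 0.75) to +4.8 points (0.439 to 0.487, ratio 3). At 10% it moves by −0.6 to +1.4 points. With the hazard unchanged, the shift of −0.3 to −1.2 points comes from back-dating alone.

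**3. Off-treatment scan interval**

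The footnote f mark stands in a column headed every 6 months, while footnote e requires scans every 12 weeks. If six months (about 26 weeks) is counted from the end of treatment, and the last on-treatment scan was up to 12 weeks earlier, the gap can reach 12 + 26 = 38 weeks. Row 7 censors progression found more than 26 weeks after the last assessment. On the six-month reading, continuing the scans would therefore not reliably recover the event.

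**The case against.** Several counter-arguments have force.

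- **Section 7.2.1 does not plainly tell sites to stop.** It also requires scans throughout time on study, and end of treatment is not end of study. This stands, but it makes the section inconsistent with itself and does not resolve the conflict.
- **Appendix 1 is general guidance.** It speaks of what is usual, allows a study to opt out, and has a censoring reason for patients not followed after treatment. But an opt-out should be clearly stated, and one that the protocol's own schedule contradicts is not.
- **A reader might infer that every stop becomes a censoring and that the result favours the drug.** The documents do not support either. Rows 3 and 6 keep clinical progression and deaths within 26 weeks as events, and row 5 censors new-therapy patients even if scans continue. The direction depends on the post-stop hazard. Applying the C2324 placebo median in full from the day of stopping is one assumption among several, and no document supports it for patients who leave after a period on drug.
- **A reader might infer that PFS will in fact differ by site.** The text permits this; nothing shows it happened.
- **The shift is small against precision.** With about 47 events, an approximate 95% interval for an exponential median of 11.04 is 11.04 × exp(±1.96/√47), or 8.3 to 14.7 months. Safety is the primary objective, and the five-year OS data also named in Protocol 2.2 are untouched. This limits the importance of the point but does not remove the contradiction.

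**Conclusion.** The contradiction stands in the current text of both documents and should be reconciled. If sites end scans when treatment stops, patients who stop without RECIST or clinical progression are censored at the last adequate scan, and so are their deaths more than 26 weeks after it.

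That censoring is informative only if the risk of progression changes after stopping. Over the assumed range, the effect on the median runs from an understatement of 0.4 months to an overstatement of 1.3 months, and is nil if the hazard is unchanged. The 6, 12 or 18 lost events per 60 patients are upper bounds. The stopping share and post-stop hazard are assumptions; the documents give neither. PFS is secondary and descriptive, so no hypothesis test or error rate is affected. The conflict itself is certain; the direction of bias is not.

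**What to change.** - In Protocol 4.1 and 7.2.1 and SAP section 3, remove unacceptable toxicity, protocol or visit deviation and other reasons for discontinuation as end points for tumour assessment.
- State that patients who stop treatment without RECIST progression continue tumour assessments until progression, death, withdrawal of consent or end of study.
- In the same edit, reconcile the off-treatment scan interval (12 weeks in footnote e, six months in the column heading) with SAP Table 2 row 7, so that progression found after stopping is not censored by the 26-week limit.

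The cost is a wording change in three places plus the interval clarification. The schedule already marks off-treatment scans, so no new type of procedure is added; how many scans this means depends on the interval settled. The small downside is that some patients keep scheduled scans after stopping, and PFS may look slightly less favourable.
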